#### 2.1.2 Secondary Objectives and Endpoints

Secondary objectives and endpoints will be assessed from time of start of USB002 or placebo infusion (Visit 1/Day 1) to Day 28.

Secondary endpoints include:

- All-cause mortality at Day 60.
- Number of ventilator-free days (defined as the number of days between Visit 1/Day 1 and Day 28 that subjects are both alive and free of mechanical ventilation [MV]; freedom from MV is further defined as free from MV for at least 48 hours after extubation).
  - In the case of repeated MV, duration of MV will be summed for the purposes of calculation. In the case of tracheostomy, the same criteria apply.
- Proportion of subjects weaned from mechanical ventilation through Day 28 (defined as free from MV for at least 48 hours after extubation. In the case of tracheostomy, the same criteria will apply). This applies only to subjects on mechanical ventilation at baseline.
- Proportion of subjects progressing from non-invasive (at baseline) to mechanical ventilation. This applies only to subjects not on mechanical ventilation at baseline.
- Time to progression (TTP) from non-invasive to mechanical ventilation.

- In the case of repeat admission to hospital and/or ICU within the first 28-days, the time from first treatment with study medication will be used to calculate TTP to MV;
- Number of days of vasoactive agent usage (defined as use of a vasoactive agent for 6 hours or more within any 24-hour period);
- Time (days) to hospital discharge;
- Changes in Ordinal Scale for Clinical Improvement (OSCI) status (see Appendix 1) from Visit 1/Day 1 to Day 28, defined as 1) time to change and 2) proportions of subjects, with 1-point and 2-point clinical status changes utilizing a time-to-event analysis from time of start of infusion (Visit 1/Day 1) of study medication to Day 28 for the time to change analysis between active and placebo groups.

### **2.1.3. Exploratory Endpoints**

For any subject that is taken off assisted ventilation and study treatment is terminated earlier than planned (96 hours in Part 1 and Day 14 in Part 2), the re-initiation of assisted ventilation will be assessed as an exploratory endpoint. In the event of re-initiation of assisted ventilation, subjects who continued receiving USB002/placebo infusion will be assessed separately to those who discontinued treatment.

## **3. STUDY DESIGN**

The study is designed as a randomized double-blind study. All staff at the site will be blinded to the treatment allocation, including Pharmacy staff, and all Sponsor personnel will also be blinded. The randomization and allocation of kits will be managed by the data management group via an interactive web randomization system (IWRS).

### Part 1

Dose escalation will be randomized, double-blinded and placebo-controlled in 24 subjects (up to 48 if DLT occurs). Up to six subjects will receive either SOC plus USB002 (n=3) or SOC plus placebo (n=3) in up to 4 escalating doses.

COVID-19 diagnosed patients in pulmonary distress requiring supplemental oxygen will be eligible for enrollment once consent has been obtained from the subject or legal representative and eligibility has been confirmed. Screening assessments obtained prior to consent and within 72 hours of infusion start will be used to assess eligibility and will not require repeating, unless determined by the Investigator as needed.

Study registration (subject number assignment) will be conducted through the IWRS upon enrollment. The Investigator will confirm eligibility and notify the pharmacy so designated study pharmacy staff can request cohort assignment and a drug kit identification randomization number through IWRS system. The pharmacy will receive dosage instructions directly from the IWRS system.

Starting at Visit 1/0 hours, subjects will receive a continuous IV infusion of USB002 or

placebo for up to 96-hours. Safety will be assessed by changes in physical examination findings, changes in vitals and laboratory parameters. AEs will be collected from the time of informed consent; those occurring between informed consent and start of infusion will be designated as medical history, and those occurring after start of infusion will be designated as AEs. Baseline assessments are defined as those conducted on Visit 1, prior to start of infusion.

Visit 5 will serve as the End of Treatment visit for Part 1. Additional visits will be conducted on Days 7, 9, 12, 14, 16, 18, 21, 24 and 28 (if/while still hospitalized). The follow-up visits on Days 28 and 60 will be conducted by phone (Telemed) upon discharge. If the subject is discharged earlier than Day 28, Telemed visits will be conducted once a week until Day 28, with the first occurring 7 days after discharge. The Day 28 Telemed visit and Day 60 Telemed visit will occur on Days 28 and 60, respectively, regardless of when the subject is discharged from hospital and the timing of their previous weekly Telemed visits.

The decision to dose-escalate, de-escalate, or increase the number of subjects in any group will be made by a Data Safety Monitoring Board (DSMB) as described in Section 6.6. Dose escalation will use the traditional 3+3 design to assess dose-response as described in Section 3.2. Assessment of progress and safety will be conducted by the DSMB, per the Safety Management Plan (SMP). If the DSMB determines there is a reasonable safety concern, enrollment may be delayed or halted. If toxicity is identified (graded according to NCI-CTCAE v5.0) at the lowest cohort level (90 ug/kg/day), DSMB may determine to de-escalate or halt the study. Escalation will continue until Part 1 enrollment is completed and the MTD is determined.

## Part 2

30 subjects will be randomized at the MTD, as determined in Part 1, to either SOC plus USB002 (n=15) or SOC plus placebo (n=15). Subjects will be treated on a continuous infusion for up to 14 days. Infusion will be discontinued at any time if  $\text{SpO}_2 \geq 94\%$  on room air is sustained for at least 48 hours. Additional visits will be conducted on Days 16 (End of Treatment visit), 18, 21, 24 and 28 (if still hospitalized). The follow-up visit on Days 28 and 60 will be conducted by phone (Telemed) upon discharge. If the subject is discharged earlier than Day 28, Telemed visits will be conducted once a week until Day 28, with the first occurring 7 days after discharge. The Day 28 Telemed visit and Day 60 Telemed visit will occur on Days 28 and 60, respectively, regardless of when the subject is discharged from hospital and the timing of their previous weekly Telemed visits.

## Parts 1 and 2

For both groups, there will be a 24-hour observation period, after infusion stop time, regardless of when this occurs and regardless of reason.

If a subject's treatment is terminated after the Visit 1/Day 1 infusion begins, for any reason, all attempts will be made to conduct all remaining study visits and assessments,

as applicable (See Tables 2 and 3). End of Treatment (Part 1 – Visit 5; Part 2 – Day 16) procedures may be conducted during the 24-hour observation period. Missed End of Treatment assessments due to disease progression or early discharge, will be considered deviations.

Respiratory evaluations will be determined by recovery landmarks of time to acceptable spontaneous breathing efforts (up to 30 minutes), termination for the need of oxygen (see Spontaneous Breathing Trial [SBT]: Appendix 2), and time to discontinuation of ventilatory assistance, if applicable. Clinical status will be evaluated using the OSCI and physical examination findings.

Follow-up for AEs with a start prior to Day 28 will be followed to resolution, stabilization, or to Day 60. Survival will be captured during the follow-up period through to Day 60, regardless of treatment or hospitalization status. AEs with a start date after Day 28 will not be captured. Any SAE that occurs at any time, through to Day 60, will be collected.

Participation will terminate for all subjects on Day 60 or at early termination due to death, consent withdrawal or lost to follow-up.

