5. If subject is discharged from hospital, Telemed visits will be conducted once a week until Day 28, with the first occurring approximately 7 days after discharge. Day 28 and Day 60 Telemed visits will occur on Days 28 and 60, respectively, regardless of discharge date and timing of previous Telemed visits. Discharged subjects will not attend the site for visits (Days 7, 9, 12, 14, 16, 18, 21, or 24, as applicable to discharge day) or undergo procedures scheduled for those visits.
6. Telephone follow-up, if discharged. Day 28 phone call window = +/- 3 days; window not applicable if still hospitalized.

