### **6.4. Reporting Procedures**

#### **6.4.1 Adverse Event Reporting**

AEs will be captured from the start of USB002/placebo infusion until Day 28 or hospital discharge, whichever occurs last. Any AEs ongoing at Day 28 (or discharge) will be followed/assessed up to the Day 60 Telemed visit. No new AEs will be collected following discharge. SAEs (new or ongoing) will be followed and/or collected until Day 60.

All AEs (whether attributable to the study drug) occurring during the study observed by the Investigator or reported by the subject will be recorded on the eCRF. The following information will be recorded for all AEs:

- Event: name/condition/diagnosis/description;
- Onset and resolution time and/or date;
- Severity;
- Relationship to study drug (assessment by staff trained and authorized to

diagnose);

- Action taken;
- Seriousness.

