8.3. Secondary Outcomes

8.3.1. All-cause mortality at Day 60.

All death data will be listed. If data applicable, the death rate at Day 60 will be summarized by total treatment groups, and by cohort and treatment group.

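### The Day 60 call may be made up to 7 days early, with no later check, so a death or SAE just before Day 60 can be missed in a discharged subject

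*Protocol*

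**What the plan says.** Collection period. Protocol Section 3 (Parts 1 and 2) states "Survival will be captured during the follow-up period through to Day 60, regardless of treatment or hospitalization status", and for serious events "Any SAE that occurs at any time, through to Day 60, will be collected". Section 6.4.1 repeats this: "SAEs (new or ongoing) will be followed and/or collected until Day 60". Section 6.4.2 also has SAEs recorded up to Day 60. Participation ends on Day 60.

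Contact schedule. Section 3 and Section 5.4.5 place the last two telephone contacts on Days 28 and 60, with weekly calls to discharged subjects only until Day 28. In Protocol Tables 2 and 3, the Day 60 column carries a window of plus or minus 7 days; the SAP schedules (Section 4.5) repeat it. The Day 28 call has its own footnote: "Day 28 phone call window = +/- 3 days; window not applicable if still hospitalized".

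Analysis. Day 60 all-cause mortality is the first-listed secondary endpoint. Protocol Section 7.2.1 treats it as a proportion. SAP Section 8.3.1 says that deaths are listed and that, if the data allow, "the death rate at Day 60 will be summarized by total treatment groups, and by cohort and treatment group". SAP Section 7.2 defines no mortality variable, and SAP Section 5.3 rules out imputation.

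**The concern.** A window that opens before the end of the observation period lets a site follow the schedule exactly and still close a subject's follow-up too soon. For someone already discharged, the Day 60 call is the only scheduled contact after Day 28. If it is made on Day 53, nothing in the schedule prompts anyone to ask what happened on Days 54 to 60. A late call does not compensate, because deaths after Day 60 fall outside the endpoint. Any error in the number of deaths and SAEs is therefore an undercount.

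What is at stake is the accuracy of the Day 60 mortality figure and of the SAE tally in a very small trial, where one event moves a percentage a long way.

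**Working it through.** **Does the 7-day window belong to the Day 60 visit?** Protocol Section 3.5 gives a maximum of 70 days on study. Screening of 72 hours (3 days) + Day 60 + an upper window of 7 days = 3 + 60 + 7 = 70. The match is exact, so the reading is sound. (The SAP title page gives about 74 days without deriving it; nothing below depends on that figure.)

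**Uncovered time.** The earliest compliant call is on Day 60 − 7 = Day 53.
- Share of the whole period: 7/60 = 11.7%.
- Share of the period after Day 28: 7/(60 − 28) = 7/32 = 21.9%.
- If calls fall evenly on the 15 days from 53 to 67, the mean loss is (7 + 6 + 5 + 4 + 3 + 2 + 1)/15 = 28/15 = 1.87 days, or 1.87/60 = 3.1%.

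**Expected missed deaths.** The documents give no mortality rate, so 60-day mortality m is an assumption, varied from 5 to 30%. The sample is n = 21, the enrollment reported in SAP Section 2.

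Under constant hazard, survival to day t is S(t) = (1 − m)^(t/60). If every call is on Day 53, the chance that a given subject's death is missed is S(53) − S(60). For m = 0.20: 0.80^(53/60) − 0.80 = 0.8211 − 0.8000 = 0.0211. Expected missed deaths are 21 × 0.0211 = 0.44, and the chance of missing at least one is 1 − (1 − 0.0211)^21 = 36%. For evenly spread calls, S(d) − S(60) is summed over d = 53 to 59 and divided by 15.

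| Assumed 60-day mortality | Missed, all calls Day 53 | Chance of missing at least one | Missed, calls spread over Days 53–67 |
|---|---|---|---|
| 5% | 0.12 | 11% | 0.03 |
| 10% | 0.23 | 21% | 0.06 |
| 20% | 0.44 | 36% | 0.12 |
| 30% | 0.62 | 47% | 0.17 |

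If deaths are concentrated early (Weibull, shape 0.5), the Day 53 column falls to 0.06, 0.12, 0.23 and 0.32. All these figures are at the upper end, because a subject still in hospital is observed directly.

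**What one missed death would do.** Cohorts 1 to 3 supply 9 USB002 subjects, and the 3 subjects of Cohort 4 add between 0 and 3. One death is then 1/12 = 8.3 to 1/9 = 11.1 percentage points of the pooled USB002 rate, and 1/3 = 33 points within a completed cohort.

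**Why the missing rule matters.** As an illustration, take 12 USB002 subjects with one recorded death, and another subject last reached alive on Day 53. Counted as a survivor, the rate is 1/12 = 8.3%. Excluded as missing, it is 1/11 = 9.1%. If that subject in fact died by Day 60, it is 2/12 = 16.7%. The SAP does not choose between the first two.

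**The case against.** The best case for the plan is that a nominal day with a tolerance is ordinary scheduling, and that the duty to collect is separate from the date of the call. Survival and SAEs are owed through Day 60 whatever the call date, and Section 4.3 has all subjects who do not withdraw consent followed to Day 60. An event that the site hears of by Day 60 can still be recorded. That stands: a reader might infer that a late event has no way into the database, and the documents do not support it. What is lacking is a scheduled check that would bring such an event to light.

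A reader might also infer that a subject called early is counted as a survivor. Neither document says so. With no imputation and no classification rule, the subject could equally be treated as missing. The undercount of events follows from the window; the bias in the rate depends on a rule that has not been written.

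A third inference is that the Day 28 window has the same fault. It does not. The Day 28 call is not the last contact: the Day 60 visit follows and lists adverse events in both parts (Sections 5.4.2 and 5.4.3). Events on Days 26 to 28 can be picked up then, with some recall delay. That window also applies only to discharged subjects, for whom any loss of non-serious events comes from the collection rules themselves. Section 6.4.1 says "AEs will be captured from the start of USB002/placebo infusion until Day 28 or hospital discharge, whichever occurs last" and also "No new AEs will be collected following discharge", while Section 3 says "AEs with a start date after Day 28 will not be captured". For a subject discharged on Day 10, the first statement collects to Day 28 and the second stops at discharge. For one discharged on Day 35, the first collects to Day 35 and the third stops at Day 28. These statements need reconciling, but changing the Day 28 window would not do it.

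Finally, the window is the same in both blinded arms, and SAP Section 7.4 plans no statistical inference. That stands too, and it limits the consequence to understated absolute counts.

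**Conclusion.** The point holds for the Day 60 contact only. The early side of its window conflicts with the commitment to capture survival and SAEs through Day 60, no later check is specified, and the SAP is silent on subjects last known alive before Day 60. Up to 7 of 60 days can be unobserved in a discharged subject, and the event counts can only be too low.

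The expected effect is small: about 0.03 to 0.17 missed deaths among 21 subjects with evenly spread calls, and 0.12 to 0.62 if every call is on Day 53. This rests on an assumed 60-day mortality of 5 to 30% and constant hazard; early-concentrated deaths would make it smaller. SAE losses cannot be sized, since the documents give no SAE rate. No test or sample size is affected. The change is worth making because it is cheap and the loss runs in one direction.

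**What to change.** 1. In Protocol Tables 2 and 3 and the SAP schedules, set the Day 60 contact window to 0 to +7 days. State that vital status and SAEs are ascertained as of Day 60, and that any call made earlier is repeated on or after Day 60. The latest permitted call is still Day 67, so the 70-day maximum is unchanged and the uncovered time falls from at most 7 days to 0.
2. Enrollment has stopped at 21 subjects, all in Part 1, so the schedule edit helps only those not yet called. For the rest, list each subject's last-contact day, re-check vital status where that day is before Day 60, and state in the SAP how a subject last known alive before Day 60 is classified in the death rate.
3. Separately, reconcile Protocol Section 6.4.1 with itself and with Section 3 on new adverse events after discharge.

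The cost is a narrower scheduling window, an occasional repeat call, one added listing and a short SAP rule. No scheduled visit is added.

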### **3.1 Study drug(s) and Control Description**

#### **3.1.1. Formulation and Appearance**

USB002 is formulated as a sterile, preservative-free, non-pyrogenic solution for injection. Formulated solution for injection consists of (Table 1):

Table 1. USB002 Formulated Solution	
Angiotensin 1-7	22.5 mg/mL
Glacial Acetic Acid, USP 	0.90 mg/mL (15 mM  )
Sodium Acetate Trihydrate, USP 	4.76 mg/mL (35 mM)
Mannitol, USP 	40.0 mg/mL (4%)
Sterile Water for Injection, USP 	quantity sufficient to 100%
Sodium Hydroxide, NF 	to pH 5
Glacial Acetic Acid, USP 	to pH 5

Millimolar[mM] National Formulary  United States Pharmacopeia

The parenteral formulation is produced as a hydrogen ion concentration (pH) buffered solution, adjusted for the proper osmolality with the addition of 4% mannitol to provide a final osmolality of 295-415 milliosmole for the dosing concentrations of A(1-7). Sterilization of USB002 is achieved via 0.22-micron filtration of the final bulk solution into the appropriate number of vials filled under aseptic conditions.

The placebo formulation will be the USB002 formulated solutions (see Table 1) without the addition of A(1-7).

### **3.1.2. Packaging and Labeling**

USB002 is packaged in a 22.5 mg/ml, single-use, stoppered 2.0 mL vial with a 2.1-mL fill.

USB002 and placebo vials will be identically labelled as 'For Investigational Use Only,' volume, kit #, and sponsor address.

### **3.1.3. Storage and Accountability Procedures**

The Investigator (or delegate) will maintain adequate records showing the receipt, dispensing, return, or other disposition of USB002/placebo, including the date, quantity, kit number, vial number and identification of subjects (number, initials as allowed) receiving study medication.

USB002/placebo will be stored securely in the institution pharmacy, where it will be prepared and provided to the study staff for infusion. USB002/placebo will be labeled with the date of preparation, subject ID#, and final dose concentration in addition to institution-required labelling.

Used vials and empty kit boxes will not be kept for accountability purposes; they will be disposed of according to the institution destruction procedures.

### **3.1.4. Dosage and Administration**

A new, unused vial will be used for each dose. The total dose administered will be dispensed per kg of body weight. USB002 or placebo will be diluted (see pharmacy manual) in saline and infused continuously by a dedicated line.

Pharmacy will prepare USB002 or placebo and provide the final product for infusion to the study team in a 100 mL sodium chloride (0.9%) Injection, *USP* bag(s). USB002 or placebo should not be administered with other medications in the same IV line and require a dedicated line. The infusion of study medication (USB002/placebo) may be piggy-backed on a 0.9% saline infusion if it is being used specifically and solely for the purpose of keeping vascular access open i.e. TKVO.

If possible, no other procedures should be performed within 90 minutes of the start of infusion; procedures or medication which may induce hypotension (BP decrease by 20% mmHg systolic) should be avoided during the same period.

### **3.1.5. Route of Administration**

USB002 or placebo will be administered by IV. The infusion rate of the reconstituted study medication/solution supplied by the pharmacist is fixed at 4.167 ml/hour (0.069 ml/min) for all dose levels and all subjects when a 100 ml infusion bag is used. The daily dose required for each subject is calculated and dispensed according to the instructions in the pharmacy manual.

### **3.2. Dose Regimen and Escalation**

#### Part 1: Dose Escalation

During dose escalation, the study will follow a traditional “3+3” design with three subjects in each cohort receiving SOC plus USB002 and three subjects in each cohort receiving SOC plus placebo. Cohorts will be enrolled sequentially for USB002 dose, with subjects receiving active drug at four sequential cohort doses of 90, 300, 600 and 900 ug/kg/day.

DSMB escalation decisions will be conducted on unblinded data. In Part 1, data review to determine dose escalation, de-escalation and study stop will be conducted by the DSMB after the last subject in each cohort has completed infusion (96-hour timepoint). Recruitment will be halted during DSMB data review for dose escalation decisions. Notification of changes in dose concentrations (escalation or de-escalation) will be issued through the IWRS.

The first 6 subjects (3 SOC plus USB002 subjects and 3 SOC plus placebo subjects) will be treated at the lowest dose. If one subject experiences an AE that is determined by the DSMB to be a potential DLT, an additional 6 subjects (3 SOC plus USB002 and 3 SOC plus placebo) will be treated at the same cohort dose. If DLTs are experienced in the new cohort at the same dose, the study may be stopped, or dose de-escalated.

DLT of hypotension (systolic BP < 90 mmHg) is a possibility, which may require the administration of fluid boluses or IV pressor agents.

At the time of a DSMB safety review, if no DLTs are identified in the first cohort, approval will be issued to treat the next 6 subjects (3 SOC plus USB002 and 3 SOC plus placebo) at the next dose. The DSMB safety reviews will be repeated between cohorts until the MTD or top dose of 900  $\mu$ g/kg/day is reached.

#### Part 2: Dose Expansion

30 subjects will be randomized to either SOC plus USB002 at the MTD established in Part 1 (n=15) or SOC plus placebo (n=15). Subjects will be treated on a continuous infusion for up to 14 days.

### **3.3. Randomization**

Randomization codes will be generated based on a central randomization schema, and the appropriate code assigned to the study kit will be issued to the Pharmacy via IWRS. Subjects will be randomized in a 1:1 ratio to receive either SOC plus USB002 or SOC plus placebo. Detailed instructions for the IWRS (enrollment/randomization/unblinding) will be provided separately.

